At Week 52, the percentages of participants in Cohorts 1 and 2 with HIV-1 RNA < 50 and < 200 copies/mL using the US FDA-defined snapshot algorithm were 77.8% (35 of 45 participants) and 82.2% (37 of 45 participants), respectively.

Change From Baseline in HIV-1 RNA

Mean (SD) baseline HIV-1 RNA values of participants in Cohorts 1 and 2 was 4.12 (1.028) \log_{10} copies/mL. The mean (SD) change from baseline in HIV-1 RNA at Weeks 26 and 52 was -2.53 (1.184) \log_{10} copies/mL, and -2.50 (1.145) \log_{10} copies/mL, respectively.

Change From Baseline in CD4 Cell Count

Mean (SD) baseline CD4 cell count value of participants in Cohorts 1 and 2 at baseline was 212 (226.2) cells/ μ L. At Week 26, mean (SD) change from baseline was 89 (106.7) cells/ μ L. At Week 52, mean (SD) change from baseline was 94 (121.5) cells/ μ L.

Preliminary Pharmacokinetic Results

A population PK (PopPK) model was developed from multiple Phase 1/2 studies to simultaneously describe IV, oral, and SC routes of administration for the GS-6207 treatment program. Data from Study GS-US-200-4625 up to Week 13 (interim PK data cut) were utilized in the PopPK model to derive posthoc exposure parameters. Following a dosing schedule of GS-6207 SC (927 mg or 2 x 1.5 mL of 309 mg/mL, administered every 26 weeks), preceded by a

14-day oral Lead-in Period, mean (%CV) GS-6207 post hoc C_{max} and C_{Week26} were 136.2 (75.2) ng/mL and 35.1 (59.2) ng/mL, respectively.

Adverse Events

Functional Monotherapy Period

During the Functional Monotherapy Period, the percentages of participants who experienced AEs were: GS-6207 37.5% (9 of 24 participants); placebo 25.0% (3 of 12 participants). Nausea was the only AE reported in > 1 participant (GS-6207 12.5%, 3 participants).

Adverse event considered related to study drugs that was reported in > 1 participant was as follows: nausea (8.3%, 2 participants; GS-6207 group).

No deaths, SAEs, AEs leading to discontinuation of study drug, or Grade 3 or higher AEs, were reported in either the GS-6207 or placebo group.

All GS-6207 Analysis

The percentage of participants who received GS-6207 in Cohorts 1 and 2 and experienced AEs was 93.1% (67 of 72 participants). The 3 most commonly reported AEs were injection site pain (37.5%, 27 of 72 participants), injection site swelling (33.3%, 24 participants), and injection site erythema (27.8%, 20 participants). Some injection site reactions (ISRs) were attributed to enfuvirtide.

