As per the PopPK modeling summarized in Section 1.2.2.7, the mean (%CV) GS-6207 post hoc C_{max} and C_{Week26} in Study GS-US-200-4334 were 93.1 (61.9) ng/mL and 22.5 (63.4) ng/mL, respectively.

Safety Results:

GS-6207 and BVY were well tolerated. By Week 54, 89.2% of participants in the GS-6207 total group (140 of 157 participants) and 96.0% of those in the BVY group (24 of 25 participants) had been exposed to study drug for at least 54 weeks.

Adverse Events

Similar percentages of participants in the GS-6207 total (total of 157 participants) and BVY (total of 25 participants) groups had any AE by Week 54 (GS-6207 total 87.9%, 138 participants; BVY 84.0%, 21 participants).

The most commonly reported AEs were as follows:

- GS-6207 total (157 participants), excluding ISRs: headache and nausea (each 13.4%, 21 participants), COVID-19 (9.6%, 15 participants), and syphilis and lymphadenopathy (each 8.9%, 14 participants)

- SC GS-6207 total (105 participants), only ISRs: injection site erythema (31.4%, 33 participants), injection site swelling (27.6%, 29 participants), and injection site pain (23.8%, 25 participants)
- Oral GS-6207 + DVY (52 participants): headache (13.5%, 7 participants), nausea and lymphadenopathy (each 11.5%, 6 participants) and COVID-19, syphilis, diarrhea, and influenza (each 9.6%, 5 participants)
- BVY (25 participants): syphilis and arthralgia (each 16.0%, 4 participants) and headache, COVID-19, back pain, weight increased, upper respiratory tract infection, and insomnia (each 12.0%, 3 participants)

The majority of the AEs reported in the 4 treatment groups were Grade 1 or 2 in severity. The percentage of participants with AEs of Grade 3 or higher was 8.3% (13 of 157 participants) in the GS-6207 total group and 8.0% (2 of 25 participants) in the BVY group. No AEs of Grade 3 or higher were reported for > 1 participant in any treatment group.

Since the Week 28 analysis, 2 additional AEs of Grade 3 or higher were reported in the GS-6207 total group (SC GS-6207 + [DVY → TAF] group: 1 participant; SC GS-6207 + [DVY → BIC] group: 1 participant) and 1 additional AE of Grade 3 or higher was reported in the BVY group (1 participant).

The percentages of participants with treatment-related AEs were as follows:

- GS-6207 total (157 participants): 43.9% (69 participants)
- SC GS-6207 total (105 participants): 58.1% (61 participants)
- Oral GS-6207 + DVY (52 participants): 15.4% (8 participants)

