- BVY (25 participants): 16.0% (4 participants)

The higher frequency of treatment-related AEs in the SC GS-6207 total group was mainly because of ISRs, as reflected in the most common AEs considered related to study drugs:

- GS-6207 total group (157 participants), excluding ISRs: nausea (5.1%, 8 participants), diarrhea and headache (each 2.5%, 4 participants), and fatigue (1.9%, 3 participants)
- SC GS-6207 total group (105 participants), only ISRs: injection site erythema (26.7%, 28 participants), injection site swelling (22.9%, 24 participants), injection site pain (19.0%, 20 participants)
- Oral GS-6207 + DVY (52 participants): nausea and diarrhea (each 3.8%, 2 participants), fatigue, headache, dyspepsia, flatulence, vomiting, weight increased, influenza, overdose, and hot flush (each 1.9%, 1 participant)

- BVY (25 participants): dyspepsia, salivary hypersecretion, insomnia, and weight increased (4.0%, 1 participant)

Overall, 57 of 103 participants (55.3%) who received SC GS-6207 had a study drug-related ISR; all were Grade 1 or Grade 2, except for 1 participant with a Grade 3 injection site nodule. There were no new Grade 3 or higher ISRs reported since the Week 28 analysis. The most frequently reported ISRs ($\geq 10\%$ in SC GS-6207 total group) and their duration in median (Q1, Q3) days were as follows:

- Injection site erythema (27.2%, 28 participants), 5 (2, 11) days
- Injection site swelling (23.3%, 24 participants), 11 (6, 29) days
- Injection site pain (19.4%, 20 participants), 4 (1, 9) days
- Injection site nodule (14.6%, 15 participants), 195 (122, 301) days
- Injection site inflammation (13.6%, 14 participants), 3 (1, 8) days
- Injection site induration (12.6%, 13 participants), 202 (101, 361) days

Overall, 15 of 103 participants had an AE of injection site nodule and 13 of 103 participants had an AE of injection site induration. All were Grade 1 or Grade 2, except for 1 participant with a Grade 3 injection site nodule. Ongoing and resolved injection site indurations and nodules were as follows:

ISRs after the first SC GS-6207 injection at Day 15:

Participant-level analysis:

- Nodules: Ongoing (1 of 11 [9.1%]); Resolved (10 of 11 [90.9%])
- Indurations: Ongoing (6 of 9 [66.7%]); Resolved (3 of 9 [33.3%])

Event-level analysis:

- Nodules: Ongoing (1 of 13 [7.7%]); Resolved (12 of 13 [92.3%])
- Indurations: Ongoing (6 of 9 [66.7%]); Resolved (3 of 9 [33.3%])

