7.2.1. Assessment of Causality for Study Drugs and Procedures

The investigator or qualified subinvestigator is responsible for assessing the relationship to study drug using clinical judgment and the following considerations:

- **No:** Evidence exists that the AE has an etiology other than the study drug. For SAEs, an alternative causality must be provided (eg, preexisting condition, underlying disease, intercurrent illness, or concomitant medication).
- **Yes:** There is reasonable possibility that the event may have been caused by the study drug.

It should be emphasized that ineffective treatment should not be considered as causally related in the context of AE reporting.

The relationship to study procedures (eg, invasive procedures such as venipuncture or biopsy) should be assessed using the following considerations:

- **No:** Evidence exists that the AE has an etiology other than the study procedure.
- **Yes:** The AE occurred as a result of protocol procedures, (eg, venipuncture)

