7.1.3. Relationship of Adverse Events to Study Drug

Related AEs are those for which the investigator selected “Related” on the AE CRF to the question of “Related to Study Treatment.” Relatedness will always default to the investigator’s choice, not that of the medical monitor. Events for which the investigator did not record relationship to study drug will be considered related to study drug for summary purposes. However, by-subject data listings will show the relationship as missing.

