7.1.7. Additional Analysis of Adverse Events

7.1.7.1. Study Drug Related Injection Site Reactions

Additional analysis of AEs will be performed for injection site reaction (ISR) related to study drug, which is defined as an AE related to study drug reported as any event within the MedDRA HLT of “Injection Site Reactions”. The following summaries will be provided for each SC injection visit (eg, Day 1, Week 28) and the overall for subjects in Treatment Groups 1 and 2.

- Number of subjects that received SC injection(s)
- Number and percentage of subjects with study drug related ISRs
- Number and percentage of subjects with study drug related ISRs by grade
- Number and percentage of subjects with study drug related ISRs by PT

The denominator for the percentage calculation for the by visit summary and the overall summary will be based on the total number of subjects who receive at least 1 SC injection at the visit of interest and the total number of subjects who receive at least 1 SC injection at any injection visit, respectively.

Duration of the ISR will also be calculated and summarized. Duration of a given ISR event is defined as the ISR stop date minus the ISR onset date plus 1 day. For ISRs with ongoing stop date, stop date will be imputed as last study date or data cut date, whichever is the earliest. Duration of ISR events in days will be summarized using descriptive statistics.

A by-subject listing for study drug-related ISRs and the corresponding duration will be provided.

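### The dedicated injection-site-reaction summaries count only drug-related events: by preferred term this drops 15% to 20% of participants with each of the three commonest reactions, and no all-cause any-ISR figure is planned

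*SAP*

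**What the plan says.** - **Dedicated ISR analysis (SAP 7.1.7.1).** The unit is the drug-related ISR, "which is defined as an AE related to study drug reported as any event within the MedDRA HLT of" injection site reactions. The counts of participants with an ISR (any, by grade, by preferred term), each by injection visit and overall, all use that set. So do the duration summary and the listing.
- **Induration and nodules (SAP 7.1.7.2).** The ongoing/resolved summaries and the duration of resolved events carry the same restriction.
- **Who decides (SAP 7.1.3).** "Relatedness will always default to the investigator’s choice, not that of the medical monitor". A blank is not a no: "Events for which the investigator did not record relationship to study drug will be considered related to study drug for summary purposes".
- **How causality is asked (Protocol 7.2.1).** Relation to study drug and relation to study procedures are two separate questions. The second is answered yes when "The AE occurred as a result of protocol procedures, (eg, venipuncture" is the example that applies.
- **General tables (SAP 7.1.6.1 and 3.2).** All treatment-emergent events, whatever their causality, are tabulated by preferred term and by severity, with a pooled column for the two SC groups. All adverse events are also listed.
- **Week 54 results (Protocol 1.2.2.8).** For the SC total group the all-cause counts are "injection site erythema (31.4%, 33 participants), injection site swelling (27.6%, 29 participants), and injection site pain (23.8%, 25 participants"). The treatment-related counts are "injection site erythema (26.7%, 28 participants), injection site swelling (22.9%, 24 participants), injection site pain (19.0%, 20 participants"). The summary figure is that "57 of 103 participants (55.3%) who received SC GS-6207 had a study drug-related ISR".

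**The concern.** Injection site reaction is named as a risk in Protocol 1.10, and Protocol 1.2.2.8 gives ISRs as the main reason why treatment-related events were more frequent in the SC groups. The tables meant to describe that risk, including when reactions occur, how severe they are and how long they last, rest entirely on a causality judgement made without blinding. Any event recorded as unrelated leaves all of them at once.

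The restriction is also easy to lose in reporting. Protocol 1.2.2.8 states it for the 55.3% figure. The list of most frequent ISRs that follows does not repeat it, and gives erythema as 28 participants (27.2%), although 33 had been reported on an all-cause basis a little earlier. A reader of that list could take a related-only rate for the rate of the reaction itself.

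**Working it through.** **Inputs**, all from Protocol 1.2.2.8: SC total group 105; participants who received an SC injection 103; all-cause counts 33, 29 and 25; related counts 28, 24 and 20; any related ISR 57.

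**1. Reproduce the stated figures.**
- All-cause: 33/105 = 31.4%, 29/105 = 27.6%, 25/105 = 23.8%.
- Related: 28/105 = 26.7%, 24/105 = 22.9%, 20/105 = 19.0%.
- Dedicated analysis: 28/103 = 27.2%, 24/103 = 23.3%, 20/103 = 19.4%; any related ISR 57/103 = 55.3%.

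All agree with the protocol. The dedicated by-term counts are the related counts, so the filter acted as the SAP describes.

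**2. Loss by term** = (all-cause − related) / all-cause.

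| Term | All-cause | Related | Dropped | Share dropped |
|---|---|---|---|---|
| Erythema | 33 | 28 | 5 | 5/33 = 15.2% |
| Swelling | 29 | 24 | 5 | 5/29 = 17.2% |
| Pain | 25 | 20 | 5 | 5/25 = 20.0% |

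Over the three terms, 15 of 87 participant-by-term counts are dropped (17.2%). Because blanks count as related, each dropped participant had that term recorded only as not related. The 15 are not necessarily 15 people: they could be as few as five.

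**3. Incidence on the injected denominator**, assuming every all-cause case was injected.
- Erythema: 33/103 = 32.0% against 27.2%.
- Swelling: 29/103 = 28.2% against 23.3%.
- Pain: 25/103 = 24.3% against 19.4%.

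The assumption can fail for at most 105 − 103 = 2 participants. If both had all three terms, the all-cause figures would be 31/103 = 30.1%, 27/103 = 26.2% and 23/103 = 22.3%.

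**4. Any-ISR figure.** A participant counts once if any ISR was related, so someone whose erythema was called unrelated still counts if another ISR was related. The overlap is not reported. From these three terms alone:
- Lower limit, all dropped participants had another related ISR: 57/103 = 55.3%.
- The dropped participants are the same five people and none had another related ISR: 62/103 = 60.2%.
- Upper limit, 15 different people and none had another related ISR: 72/103 = 69.9%.

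**5. What the general tables supply.** SAP 7.1.6.1 gives all-cause counts by term and by severity within term. It gives no any-ISR total, no any-ISR grade distribution, no split by injection, no duration and no ongoing/resolved status.

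**The case against.** The case for leaving the plan alone is substantial. The section is headed as study-drug related, it is an additional analysis in a Phase 2 trial that SAP 3.5 calls non-confirmatory, and it sits beside complete all-cause tables. The protocol itself reports the all-cause counts before the related ones. Protocol 7.2.1 allows a no on drug causality only where there is evidence of another cause. All of this is correct, and it narrows the gap to the items in step 5 of the working.

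The filter also has a use. In GS-US-200-4625, "Some injection site reactions (ISRs) were attributed to enfuvirtide", and separating sources was sensible there. Here SC lenacapavir is the only injected study drug, so a reader might infer that the filter separates nothing. The documents do not support that. Protocol Appendix 4 permits injectable progesterone, and SAP Appendix 3 (item 15) assigns an ISR to an injection visit by start date alone, up to the next injection. In these tables, relatedness is the only guard against counting a reaction to a non-study injection. That is a good reason to keep the related rows, but not to show them alone.

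A reader might also infer that the dropped events were blamed on the injection procedure instead of the drug. The two questions are separate and both can be answered yes. The procedure examples do not include study-drug injection, and the documents do not say why any of these events was judged unrelated.

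**Conclusion.** The point holds by preferred term. The dedicated ISR summaries omit five participants for each of the three commonest reactions, 15% to 20% of those who had them, or about five percentage points on 103 injected participants. The percentages on 103 assume that every case was injected; the counts themselves need no assumption.

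It is tempting to carry this over and say that the 55.3% leaves out about one participant in six. The documents do not support that. A shortfall of exactly one in six would require 57/(5/6) = 68.4 participants, or 66.4% of 103, which the counts neither show nor exclude. The loss may be zero. The range of 55.3% to 69.9% uses these three terms only; unrelated events under other terms are not reported.

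Nor are the all-cause data hidden: counts by term and by severity are planned and reported. The gap is the missing all-cause any-ISR total (overall and by grade), the by-injection split, and the duration and ongoing/resolved summaries. That the effect on the any-ISR figure cannot be worked out from the documents is itself a reason to tabulate it. This is an inexpensive improvement to the reporting of a named risk, not a correction of an error.

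**What to change.** In SAP 7.1.7.1 and 7.1.7.2, keep the study-drug-related rows as they are. Beside them, add all-cause rows for any treatment-emergent event in the injection site reactions HLT with onset on or after an SC lenacapavir injection. Show these overall, by injection visit, by grade and by preferred term, with duration and, for induration and nodules, ongoing/resolved status, on the same injected denominator. List the events judged unrelated with any recorded alternative cause; Protocol 7.2.1 requires one only for serious events, so many entries may be blank. Label each ISR percentage in the report as related or all-cause.

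The Week 54 results are already summarised in the protocol. The rows can be added to the Week 80 and final analyses and produced for Week 54 as a supplement, with the change documented in the clinical study report as SAP Section 1 provides.

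The cost is a few table rows from data already collected and a possibly less favourable ISR rate. The all-cause rows may also include some reactions to non-study injections, which is why both sets should be shown.

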The median (Q1, Q3) duration of resolved injection site nodule and injection site induration was 278 (136, 366) days and 202 (101, 213) days, respectively.

ISRs after the second SC GS-6207 injection at Week 28:

Participant-level analysis:

- Nodules: Ongoing (5 of 8 [62.5%]); Resolved (3 of 8 [37.5%])
- Indurations: Ongoing (3 of 6 [50.0%]); Resolved (3 of 6 [50.0%])

Event-level analysis:

- Nodules: Ongoing (5 of 8 [62.5%]); Resolved (3 of 8 [37.5%])
- Indurations: Ongoing (3 of 6 [50.0%]); Resolved (3 of 6 [50.0%])

The median (Q1, Q3) duration of resolved injection site nodule and injection site induration was 152 (123, 240) days and 145 (4, 258) days, respectively.

CONCLUSIONS:

The conclusions from the Week 54 interim analysis of Study GS-US-200-4334 are as follows:

- High rates of virologic suppression continued to be maintained through Week 54. For the primary efficacy end point, overall, 136 of 157 participants (86.6%) who received SC or oral GS-6207 and 23 of 25 participants (92.0%) who received BVY had HIV-1 RNA < 50 copies/mL at Week 54.
- For participants with HIV-1 RNA < 50 copies/mL at Week 28, high rates of virologic suppression continued to be maintained through Week 54.
- Subcutaneously and orally administered GS-6207 remained generally safe and well tolerated.

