7.1.7.2. Study Drug Related Injection Site Induration and Nodules

Percentage of ongoing and resolved study drug related injection site induration will be summarized for each SC injection (eg, Day 15, Week 28, and Week 54) and the overall at both subject-level and event-level.

For the subject-level summary, if a subject had more than one injection site indurations, the subject will be counted in the “Ongoing” category unless all study drug related injection site induration events have been resolved.

For the event-level summary, duration of the resolved events will be summarized using descriptive statistics.

Study drug related injection site nodules will be summarized in the same manner as defined for study drug related injection site induration.

A by-subject listing for study drug related injection site induration and nodules and the corresponding duration will be provided.

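### Ongoing injection site nodules and indurations are treated as ended, or dropped, when duration is summarized, which understates how long these reactions last

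*SAP*

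**What the plan says.** SAP 7.1.7.1 defines the duration of an injection site reaction (ISR) as stop date minus onset date plus 1 and summarizes it with descriptive statistics. For events without a stop date it says: "For ISRs with ongoing stop date, stop date will be imputed as last study date or data cut date, whichever is the earliest".

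SAP 7.1.7.2 adds a summary for indurations, and in the same manner for nodules. It tabulates the percentage ongoing and resolved for each injection and overall, at subject and event level. On duration it says: "For the event-level summary, duration of the resolved events will be summarized using descriptive statistics".

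Neither section uses a method for censored times. Protocol 1.2.2.8 summarizes this study's Week 54 results. The overall row for induration reads "Injection site induration (12.6%, 13 participants), 202 (101, 361) days".

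**The concern.** An ongoing event has lasted at least as long as its follow-up, and its true duration is unknown. Giving it a stop date at the cut-off replaces the true duration T by min(T, C), where C is follow-up time. That can never exceed T, so the mean and every quantile are at or below the truth. Using resolved events only conditions on T ≤ C, which favors short events when censoring is independent of duration.

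Nodules and indurations are the long-lasting local reactions. Protocol 7.6.4 singles out reactions that persist beyond 26 weeks, naming these two in particular. Neither planned duration summary estimates the share of events that last that long.

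**Working it through.** **Ongoing events** (Protocol 1.2.2.8, event level)

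| | First injection | Second injection | Pooled |
|---|---|---|---|
| Indurations ongoing | 6/9 = 66.7% | 3/6 = 50.0% | 9/15 = 60.0% |
| Nodules ongoing | 1/13 = 7.7% | 5/8 = 62.5% | 6/21 = 28.6% |

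The group percentages match those printed in the protocol.

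**Recovering the resolved durations.** After the first injection: "The median (Q1, Q3) duration of resolved injection site nodule and injection site induration was 278 (136, 366) days and 202 (101, 213) days". After the second, for nodule and then induration: "injection site induration was 152 (123, 240) days and 145 (4, 258) days". Each induration summary rests on 3 resolved events. With 3 values, the SAS default quartiles are the minimum, middle and maximum. Interpolated quartiles are ruled out, because they would make the shortest second-injection value 2 × 4 − 145 = −137 days. The six resolved indurations are therefore 4, 101, 145, 202, 213 and 258 days, with median (145 + 202)/2 = 173.5.

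**Placing the ongoing times.** Assume that the overall row follows 7.1.7.1 and holds these 15 events. Its quartiles are then the 4th, 8th and 12th ordered values: 101, 202 and 361. Apart from ties, the nine ongoing times must be two up to 101, two between 101 and 202, one between 202 and 361, and four at 361 or more. No listed resolved induration exceeds 258 days, so the 361 is a follow-up time.

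**Kaplan-Meier, one consistent placement.** Ongoing times of 50, 80, 150, 170, 300, 361, 400, 400 and 400 reproduce 101/202/361.

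| Day | At risk | S(t) |
|---|---|---|
| 4 | 15 | 14/15 = 0.933 |
| 101 | 12 | × 11/12 = 0.856 |
| 145 | 11 | × 10/11 = 0.778 |
| 202 | 8 | × 7/8 = 0.681 |
| 213 | 7 | × 6/7 = 0.583 |
| 258 | 6 | × 5/6 = 0.486 |

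The median is 258 days, and 77.8% are unresolved at 182 days.

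**All consistent placements on a grid of cut points (1,800).** S(182) ranges from 0.75 to 0.79, and S just after day 258 from 0.44 to 0.51. The median is 258 days in 1,760 placements and not reached in 40. Under the imputed rule, 8/15 = 53% to 10/15 = 67% of durations exceed 182 days.

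**First-injection indurations alone.** The resolved-only median of 202 days comes from 3 of 9 events. If all six ongoing events were censored at day 182, S(202) = 8/9 × 1/2 = 0.44 and the median is 202. If all were followed beyond day 213, S = 8/9 × 7/8 × 6/7 = 0.67 and the median is not reached. If the six share one follow-up time of 182 or 360 days, the 7.1.7.1 median equals that time.

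**Second-injection nodules** (resolved 123, 152 and 240; 5 ongoing). The Kaplan-Meier median runs from 152 days to not reached, depending on follow-up.

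**Simulated size** (1,000,000 exponential durations; follow-up uniform on 180 to 540 days; both assumed)

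| True median | Ongoing | Imputed rule | Resolved only |
|---|---|---|---|
| 100 | 11% | 100 | 86 |
| 200 | 31% | 191 | 123 |
| 365 | 52% | 250 | 146 |

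**The case against.** - **The percentage ongoing is reported.** SAP 7.1.7.2 does not hide ongoing events, and its duration is labelled as that of resolved events. This stands, and it makes the resolved-only figure easier to read correctly. It does not correct either median.
- **The overall row may hold unlisted events.** Third-injection indurations (Week 54) could be included. A random search with two extra events gave Kaplan-Meier medians from 213 days to not reached and S(182) from 0.64 to 0.81. With four, the ranges were 202 days to not reached and 0.59 to 0.82. Most sets still gave 258 days or not reached. The direction is unaffected, but 258 days and 75 to 79% are conditional on the 15-event assumption.
- **Precision is poor.** For the placement tabulated above, the 95% log-log interval for S(182) is 0.46 to 0.92. Placements elsewhere on the grid go down to 0.41, and the interval for the median runs from 145 days to not reached. This stands, and Kaplan-Meier would show it, whereas a median from 3 of 9 events does not.
- **The bias can be small.** At a true median of 200 days the simulated imputed rule is under 5% low.
- **The missing note is judged from a protocol summary.** The full report table is not available and may carry a footnote. This stands.
- **This is descriptive safety output in a non-confirmatory Phase 2 trial, and both overall medians (195 and 202 days) already exceed 182.** This is fair. It argues against calling the point critical, but a reported safety figure should still not be biased when the remedy is one table.

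**Conclusion.** The concern holds. The imputed rule cannot overstate duration, and the resolved-only rule is biased short under independent censoring. Resolved-only is the more biased of the two here, but it is labelled.

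The effect matters for indurations after both injections and for second-injection nodules. It is small for first-injection nodules (1 of 13 ongoing) and negligible for erythema, swelling and pain, whose medians are 4 to 11 days. For pooled indurations, the best reading of the listed figures is a median of 258 days or more, against 202 as reported, with about three quarters unresolved at 26 weeks. The direction is firm. The sizes rest on the 15-event assumption and on few events. This should be changed, but it does not touch the primary endpoint.

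**What to change.** For nodules and indurations, summarize time to resolution by Kaplan-Meier, with ongoing events censored at the earlier of last study date and data cut date. Do this by preferred term overall, and by injection where event numbers allow. Report the median with its confidence interval (or state that it is not reached) and the percentage unresolved at 26 weeks. Add 52 weeks only where follow-up supports it. Use this in place of the imputed-stop-date duration for these two terms. Keep the resolved-only duration and the percentage ongoing as labelled supplements, and leave the other reactions as planned. The Week 80 and final analyses can adopt the same rule.

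The cost is a change of SAP wording and one standard table on dates already collected. The drawbacks are few events per term and injection (6 to 13), several events in some participants (13 first-injection nodules in 11 participants), wide intervals, and longer reported durations.
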